CLINICAL TRIALS OFFICE 
Medical College of Wisconsin Cancer Center Clinical Trials Office (CTO) [name] Milwaukee, WI 53226 [contact] [contact] Email: [contact]
 
Administrative Director [name], BSN, RN, CCRP
	COLLABORATORS 
PINNACLE BIOLOGICS INC. [name] [contact] [contact] Email: [contact]
 
A United States based subsidiary of: CONCORDIA LABORATORIES INC. [name] Tel: [name] [contact] Email: [contact]

PROTOCOL SYNOPSIS

Protocol Identifiers.	ClinicalTrials.gov ID: NCT01966809 IND No.: 104,613 MCW/FH IRB: PRO00023580 MCW GC: FP00005327
Title	A Phase II Study of Photodynamic Therapy (PDT) with Photofrin® (IND 104,613) for Recurrent High-Grade Gliomas in Adults
Principal Investigator	[name]
Protocol Investigators	Please refer to page 4 of the protocol.
Sponsor(s) & Collaborators	Sponsor-Investigator: [name] Industry Collaborator: Pinnacle Biologics Inc.
Institution(s)	Medical College of Wisconsin/Froedtert Hospital
IND Number(s)	
Name of Approved Investigational Drug(s)	Hematoporphyrin Derivatives (HPDs) Photofrin® (porfimer sodium, 75 mg) for Injection
Name of Approved Investigational Devices(s)	Angiodynamics DIOMED 630 PDT Laser Laserscope KTP/532® Surgical Laser System(Series 800) ^A Laserscope KTP YAG® Surgical Laser System (Series 800) ^A ^A Pending FDA Approval
Dose of Investigational Drug	2.5 mg kg ⁻¹ Photofrin® (porfimer sodium, 75 mg) for Injection 240 J cm ⁻² Laser light (630 nm)
Route of Administration	Investigational Drug: Intravenous Injection (IV), over 3 to 5 minutes Photodynamic Therapy: Intraoperative Photoillumination
Study Population/ Treatment Group(s)	Single Arm, adult patients with recurrent high-grade gliomas will receive one dose of Photofrin® and PDT during the time of clinically indicated tumor resection surgery.
Sample Size	30 Adult patients
Selection of Study Patients	30 adult patients with high-grade recurrent gliomas will be referred to and/or screened at the MCW/FH Cancer Center. Patients will be reviewed by the Neuro-Oncology Brain Tumor Board and determine if tumor resection will be part of their clinically indicated plan of care. An investigative team member and a neuro-oncologist will determine if potential patients meet the inclusion and exclusion eligibility criteria as defined in the protocol.

Inclusions Eligibility Criteria	
 1. Age: ≥ 18 years 2. Disease: Patients with relapsed or refractory high-grade glioma are eligible. Patients must have had histologic verification of malignancy at original diagnosis or relapse. Tumors must be supratentorial in location. 3. Disease Status: Patients must have potentially resectable disease. 4. Therapeutic Options: Patients' current disease state must be one for which there is no known curative therapy or therapy proven to prolong survival with an acceptable quality of life. 5. Performance Level: Karnofsky $\geq 50\%$ 
Note: Neurologic deficits in patients with CNS tumors must have been relatively stable for at least 7 days prior to study enrollment. Patients who are unable to walk because of paralysis, but who are up in a wheelchair, will be considered ambulatory for the purpose of assessing the performance score.
 6. Predictable Life Expectancy: > 8 weeks 7. Prior Therapy: Patients must have fully recovered from the acute toxic effects of all prior anti-cancer chemotherapy. At least three weeks from previous chemotherapy and 4 weeks from prior radiation therapy 
Note: Although clinical determination of true progression vs. pseudoprogression may be difficult within the first 12 weeks following radiation and/or chemotherapy, qualified candidates need only be 4 weeks out from prior radiation and/or chemotherapy, a common standard of other recurrent glioma trials.
 8. Organ Function: 
 a. Adequate bone marrow function 
 i. Absolute neutrophil count $\geq 1,000$ ii. Platelet count $\geq 100,000$ (may transfuse to meet requirement) b. Adequate renal function 
 i. Creatinine clearance or radioisotope GFR $\geq 70-60$ mL/min/1.73 m² c. Adequate liver function 
 i. Bilirubin (direct) $\leq 3X$ upper limit of normal (ULN) for age ii. SGPT (ALT) $\leq 10X$ ULN 
 1. For the purpose of this study, the ULN for SGPT is 45 U/L ii. Serum albumin ≥ 2 g/dL d. Adequate coagulation 
 i. PT and INR $\leq 2X$ ULN, per institutional guidelines 9. Central Nervous System Function: Patients with seizure disorder may be enrolled if receiving non-enzyme inducing anticonvulsants and well controlled. 10. Informed Consent: All patients or legally authorized representatives must sign a written informed consent according to institutional guidelines. 11. All available archival tumor tissue slides disease evaluations should be reviewed by a Froedtert Health-MCW neuropathologist prior to study enrollment.
--	---

Exclusion Eligibility Criteria	
 1. Disseminated disease 2. Pregnancy or Breast-Feeding: Pregnant or breast-feeding women will not be entered on this study, as risks of fetal and teratogenic adverse effects of Photofrin® are not known. 3. Other concurrent tumor therapy 4. Subjects with porphyria 5. Subjects taking potentially photosensitizing drugs (Appendix 3) 6. The presence of adverse events of neurologic function, photosensitivity, or photophobia Grade 4 or higher (CTCAE Version 4.0)⁴⁷ 7. Allergy to eggs, soybean oil, or safflower oil (due to potential allergy against intralipids) 8. Patients who in the opinion of the investigator may not be able to comply with the safety monitoring requirements of the study are not eligible.
Estimated Length of Study	Patients will be followed up for 3 years following their PDT treatment. Accrual Period is projected to take 3 years with an average of 10 patients enrolling annually.
Regimen	Patients will be give one regimen of the investigational drug for PDT at the time of normal tumor resection for recurrent, high-grade gliomas
Design	Single Arm, Phase II Study
Multicenter	No
Blinding	None
Randomization	None
Primary Objective(s)	
1.1.1 To estimate the six-month relapse-free survival (RFS) distribution in adults with recurrent gliomas

Secondary Objective(s)	
1.2.1 To further explore and report descriptively the safety and tolerability of photodynamic therapy (PDT) in adults with recurrent glioma tumors
 
1.2.2 To obtain preliminary data toward determining whether this combination results in higher remission rate when compared to historical data
 
1.2.3 To further explore and report progression-free survival and overall survival for three years post PDT treatment
 
1.2.4 To measure complete response, partial response, stable disease or progressive disease using the response assessment for Neuro-Oncology (RANO) criteria with the follow-up medical imaging, which specifically incorporates volumetric measurements of brain tumor enhancement and clinical measures of neurological decline and to compare these outcomes to historical controls

Other Outcomes of Interest	None at the time

PROTOCOL REVISION HISTORY

Version No.	Revision Date	Summary of Changes
1.0	01/15/2013	Version of the Original Submission (OS)
1.1	05/10/2013	Changes Requested by the MCW/FH IRB, Letter Dated 11/07/2013 
 ▪ Removed References to Avastin from the protocol ▪ Administrative Changes/Updates
2.0	07/14/2014	Protocol Reformatting Overhaul for the Cancer Center CTO 
 ▪ Addition of the following protocol sections: 
 ➢ Title page ➢ Table of Contents ➢ Study Committee page ➢ Protocol Synopsis ➢ List of Abbreviations ➢ 7.0 Investigational Drug and Device Information ➢ 10.0 Statistical Considerations ➢ 11.0 Evaluation Criteria ➢ 12.0 Adverse Event Reporting Requirements ➢ 13.0 Study Data Collection and Safety Monitoring ➢ 14.0 Conduct of Study ➢ Appendix 4 Overview of Published Literature: Photodynamic Therapy ▪ Reformatted Sections from Letters (A, B, C,.. etc.) to Numbers (1, 2, 3, ... etc.) ▪ Target Accrual updated from 12-18 patients to 30 patients
2.0	08/08/2014	Changes Requested by the FRC on 07/22/2014 and 08/04/2014 Changes Requested by the SRC on 06/16/2014 
 ▪ Administrative Updates were made to the following sections 
 ➢ Section 1.0: Reformatted Primary and Secondary Objectives ➢ Section 2.6: Titles were provide for subsections 2.6.1, 2.6.2, 2.6.3 ➢ Section 3.4: Updated to clarify screening and eligibility process ➢ Section 6.7: Clarification of use of other investigational agents ➢ References: Reference numbered 59 to 73 were added ▪ Section 3.2 
 ➢ Clarification of Protocol Screening Process to avoid treatment of necrosis and/or pseudoprogression ▪ Section 5.7.1 
 ➢ Clarification of Study Endpoints, Tests and Procedures ▪ Section 6.2 
 ➢ Included specifications for monitoring pulse oximetry ▪ Appendix 1 
 ➢ Updates were made to clarify protocol specific procedures, observations, and EHR data collection of the patients' standard of care

Version No.	Revision Date	Summary of Changes
2.0	08/29/2014	
Changes Requested by the SRC on 08/21/2014
 
 ▪ Section 2.3: Additional background added to clarify the dose of Photofrin® ▪ Section 5.1.1: Table of Study Specific Procedures added for Clarification ▪ Section 5.1.3: Updated to clarify that patients will receive Photofrin® in the Adult Translational Research Unit ▪ Section 5.1.6: Administrative update for clarification ▪ Section 5.1.7: Administrative update to account for the occurrence of weekends and holidays ▪ References: : Addition of reference number 73
2.0	10/30/2014	
Addition of Data Safety Monitoring Plan for DSMC Review
 
 ▪ Title page: Clarification of clinical trial funding and support ▪ Title page: Change to MCW/FH IRB protocol number ▪ Table of Contents: Administrative updates ▪ Study Committee: Administrative updates to Nonemergency Contact ▪ Study Committee: Administrative updates to Collaborators Information ▪ Protocol Synopsis: Update to new MCW/FH IRB protocol number ▪ Protocol Synopsis: Clarification to Selection of Study Patients ▪ Section 7.1.7: Administrative updates to Collaborators Information ▪ Section 12.3: Administrative change to section title ▪ Section 12.6.1: Clarification provided for Reporting to the MCW/FH IRB ▪ Section 12.6.2: Clarification provided to guide reader where to look for expedited reporting to the DSMC ▪ Section 13.3.2: Addition/Clarification Expedited Reporting in the Data Safety Monitoring Plan ▪ Section 13.3.3: Interim Analysis and Stopping Guidelines section added to the Data Safety Monitoring Plan ▪ Section 13.3.3: Safety Monitoring and Stopping Guidelines section added to the Data Safety Monitoring Plan ▪ Section 13.4.1: Administrative formatting update ▪ Section 13.4.2: Administrative formatting update ▪ Section 13.5: Study records will be retained for 10 years per the MCW/FH IRB SOP
2.0	12/01/2014	
Administrative Update for MCW/FH IRB and FDA Review
 
 ▪ Section: Protocol Revision History Added/Completed ▪ ICF: Replaced 'Clinical Cancer Center' with 'Hope Clinic' ▪ ICF: Update Information regarding blood clotting risks

LIST OF ABBREVIATIONS

AE	adverse event
ALT	Alanine Aminotransferase
ANC	absolute neutrophil count
AST	aspartate aminotransferase
AUC	area under the concentration time curve
BP	blood pressure
BUN	blood urea nitrogen
CI	confidence interval
CNS	central nervous system
CR	complete remission
CrCl	creatinine clearance calculator
CRF	case report forms
CTCAE	Common Terminology Criteria for Adverse Events
CTEP	Cancer Therapy Evaluation Program
CTMS	Clinical Trials Management System
CTO	Clinical Trials Office
DFS	disease free survival
DLT	dose limiting toxicity
DSMC	data safety monitoring committee
DSMP	data safety monitoring plan
ECHO	echocardiogram
EFS	event free survival
EP	European Pharmacopeia
FISH	fluorescence in situ hybridization
FRC	Faculty Review Committee
GFR	glomerular filtration rate
HgB	hemoglobin
HpD	hematoporphyrin derivative
HSV	herpes simplex virus
IRB	Institutional Review Board
LDH	lactate dehydrogenase
MCW	Medical College of Wisconsin
MFC	multiparameter flow cytometry
MRD	minimal residual disease
MTD	maximum tolerated dose
MRI	magnetic resonance imaging
MUGA	multi gated acquisition scan

NOS	not otherwise specified
NRM	non-relapse mortality
NS	normal saline
OnCore™	Online Enterprise Research Management Environment
ORR	overall response rate
OS	overall survival
PCP	pneumocystis carinii pneumonia
PCR	polymerase chain reaction
PDT	photodynamic therapy
PFS	progression free survival
PI	principal investigator
PR	partial response
PS	photosensitizer
RFS	recurrence free survival
SAE	serious adverse event
SIRS	systemic inflammatory response
SRC	Scientific Review Committee
ULN	upper limit of normal
UPIRSO	unanticipated problems involving risks to subjects or others
USP	United States Pharmacopeia
WBC	white blood count

1.0 GOALS AND OBJECTIVES/SCIENTIFIC AIMS

Primary Objectives/Aims

- 1.1.1 To estimate the six month relapse-free survival (RFS) distribution in adults with recurrent gliomas

1.2 Secondary Objectives/Aims

- 1.2.1 To further explore and report descriptively the safety and tolerability of photodynamic therapy (PDT) in adults with recurrent glioma tumors
- 1.2.2 To obtain preliminary data toward determining whether this combination results in higher remission rate when compared to historical data
- 1.2.3 To further explore and report progression-free survival and overall survival for three years post PDT treatment
- 1.2.4 To measure complete response, partial response, stable disease or progressive disease using the response assessment for Neuro-Oncology (RANO) criteria with the follow-up medical imaging, which specifically incorporates volumetric measurements of brain tumor enhancement and clinical measures of neurological decline and to compare these outcomes to historical controls

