10.2 Sample Size and Study Duration

The sample size is based on a single-arm phase II study designed to detect an increase in the 6-month relapse-free survival rate from the historical value of 35% (treated as fixed) to 55%. With 29 subjects with known 6-month outcome, the study will have 80% power to detect such an increase at a one-sided 10% significance level. This calculation is slightly conservative, because

it does not incorporate the increase in the estimated survival rate from censored observations, thus the actual power might be slightly higher. A censoring rate of less than 5% is expected, so 30 patients will be enrolled in the study. The following table shows the estimated power of the study under various hypothetical values of 6-month relapse-free survival.

6-month RFS	Power
45%	43%
50%	64%
55%	82%
60%	93%
65%	98%

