10.4 Methods of Analyses for Secondary Objectives

In this single arm phase II trial, the secondary objectives are considered exploratory and will be reported descriptively based on appropriate statistical methods and accounting for patients who may undergo additional anticancer therapy post documentation of a sustained objective response. It is not possible to determine how many patients will provide data that may be used to address each of the secondary objectives. Central review histological diagnoses will be compared with diagnoses reported by the treating site. We will assess the potential impact of any differences on primary conclusions of this study. Considerations will be accounted for when making comparisons of survival and disease free survival for recurrent glioma patients. Refer to Appendix 4

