11.3 Response Criteria

Secondary outcomes will be measured using the response assessment for Neuro-oncology (RANO) criteria⁵⁸ applied to follow-up medical imaging. Specifically, complete response, partial response, stable disease or progressive disease will be determined using volumetric measurements of brain tumor enhancement and clinical measures of neurological decline.

1. Complete response requires all of the following: complete disappearance of all enhancing measurable and nonmeasurable disease sustained for at least 4 weeks; no new lesions; stable or improved nonenhancing (T2/FLAIR) lesions; patients must be off corticosteroids (or on physiologic replacement doses only); and stable or improved clinically. Note: Patients with nonmeasurable disease only cannot have a complete response; the best response possible is stable disease.
2. Partial response requires all of the following: > 50% decrease compared with baseline in the sum of products of perpendicular diameters of all measurable enhancing lesions sustained for at least 4 weeks; no progression of nonmeasurable disease; no new lesions; stable or improved nonenhancing (T2/FLAIR) lesions on same or lower dose of corticosteroids compared with baseline scan; the corticosteroid dose at the time of the scan evaluation should be no greater than the dose at time of baseline scan; and stable or improved clinically. Note: Patients with nonmeasurable disease only cannot have a partial response; the best response possible is stable disease.
3. Stable disease will require all of the following: does not qualify for complete response, partial response, or progression; stable nonenhancing (T2/FLAIR) lesions on same or lower dose of corticosteroids compared with baseline scan. In the event that the corticosteroid dose was increased for new symptoms and signs without confirmation of disease progression on neuroimaging, and subsequent follow-up imaging shows that this increase in corticosteroids was required because of disease progression, the last scan considered to show stable disease will be the scan obtained when the corticosteroid dose was equivalent to the baseline dose.

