APPENDIX 4: OVERVIEW OF PUBLISHED LITERATURE: PHOTODYNAMIC THERAPY

Reference	[Study Phase] ▪ Approach	N	Type of Brain Tumor			Photosensitizer [Dose]	Light Density [J/cm ²]	Median Overall (Progression Free) Survival [months]		
			GBM	AA	Other			Group ID	Primary	Recurrent
Stupp⁵⁹ ▪ TMZ	[phase 3]	573	Control 287					Control	12.1 (5.0)	
			TMZ 286					TMZ	14.6 (6.9)	
Akimoto⁶⁰ ▪ i/o cavitary spot	[case series]	14	10		4	Talaporfin sodium [40 mg m ⁻³]	27		26 (23)	9 (3)
Muragaki⁶¹ ▪ i/o cavitary spot	[case series]	22	13	3	6	Talaporfin sodium [40 mg m ⁻³]	27	27.9 (20)	24.8 (12)	
Stylli⁶² ▪ i/o cavitary Intralipid pool	[case series]	136	78	58		Hematoporphorin derivative (HpD) [5 mg kg ⁻¹]	70-240	GBM	14.3	13.5
								AA	76.5	66.6
Rosenthal⁶³ ▪ i/o cavitary Intralipid pool	[phase 1]	28	16	8		Boronated porphyrin (BOPP) [0.25-8 mg kg ⁻¹]	25-100	GBM	5	11
								AA		18
Schmidl³ ▪ i/o cavitary balloon	[phase 1]	20	5	3	12	Photofrin [®] [0.75 - 2.0 mg kg ⁻¹]	100			
Stummer⁶⁴ ▪ FGR	[phase 3]	243	Control 115		Control 16	5-ALA [20 mg kg ⁻¹]		Control	13.5 (3.6)	
			FGR 122		FGR 17			FGR	15.2 (5.1)	
Beck⁶⁵ ▪ interstitial	[case series]	10	10			5-ALA [20 mg kg ⁻¹]				15
Kostron⁶⁶ ▪ i/o cavitary superficial & interstitial	[case series]	58	50			HpD [2.5 mg kg ⁻¹]	250		19	7
Kostron⁶⁷ ▪ i/o cavitary balloon or diffusor	[phase 3]	52	Control 26			Foscan (mTHPC) [0.15 mg kg ⁻¹]	20		3.5	
			PDT 26						8.5	
Eljamal⁶⁸ ▪ FGR post-operative cavitary	[phase 3]	27	Control 14			5-ALA FGR Photofrin [®] PDT [20 mg kg ⁻¹ 2 mg kg ⁻¹]	100	Control	5.6 (4.8)	
			PDT 13					PDT	12.2 (8.6)	
Lyons⁶⁹ ▪ FGR post-operative cavitary ▪ repetitive balloon ▪ IORT	[phase 2]	73	ST 25			5-ALA FGR Photofrin [®] PDT [20 mg kg ⁻¹ 2 mg kg ⁻¹]	100	ST	4.6	
			ST+ PDT 13					ST+PDT	9.2	
			ST+IORT 18					ST+IORT	11.2	
			ST+PDT+IORT 17					ST+PDT+IORT	18.2	
Muller^{71, 70} ▪ unknown	[phase 3]	77	Control 34			Photofrin [®] [2 mg kg ⁻¹]	120	Control	8	
			PDT 43					PDT	11	
Muller⁷² ▪ i/o cavitary balloon & fiber	[case series]	96	49	24	26	Photofrin [®] [2 mg kg ⁻¹]	58 ± 17	GBM	7.6	6.7
								Non-GBM	15.5	13.8

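### Objectives 1.2.2 and 1.2.4 compare remission and response with history, but the plan gives no historical response rate, and the rate it would produce reflects surgery whichever MRI is the baseline

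*Combined protocol and SAP*

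**What the plan says.** Objective 1.2.2 (Section 1.2 and the Synopsis) is to gather preliminary data on "whether this combination results in higher remission rate when compared to historical data". Objective 1.2.4 is to classify patients as CR, PR, SD or PD by RANO and "to compare these outcomes to historical controls". Neither gives a rate or a source.

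Section 10.4 calls the secondary objectives exploratory and descriptive, and says the number of contributing patients cannot be determined. Its one pointer to outside data reads: "Considerations will be accounted for when making comparisons of survival and disease free survival for recurrent glioma patients. Refer to Appendix 4". The outcome heading in Appendix 4 is "Median Overall (Progression Free) Survival [months"].

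Section 11.3 defines complete and partial response, not remission. The only link is the abbreviation list, which expands CR as "complete remission". For partial response, Section 11.3 adds: "Patients with nonmeasurable disease only cannot have a partial response; the best response possible is stable disease". It makes the same note for complete response. Section 11.2 measures response against the pretreatment baseline.

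Under Sections 5.1.4 and 5.1.5, every patient has as much tumor removed as is neurologically safe, and the cavity is then illuminated.

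**The concern.** A historical comparison needs a rate to compare with and a measurement that means the same thing on both sides. The plan supplies neither for remission or response. The reference rate would have to be chosen after the trial's own rate is known.

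Resection is also part of the treatment sequence, so change in enhancing tumor depends heavily on how much the surgeon removed. A response rate above or below some published figure could be read as evidence about PDT when it mainly reflects extent of resection and the choice of baseline scan.

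**Working it through.** **1. The plan's own figure.** The only numerical design is for 6-month relapse-free survival (RFS), in Section 10.2: an increase "from the historical value of 35% (treated as fixed) to 55" percent, with 29 evaluable patients and one-sided 10% significance. Exact binomial with success at 14 or more of 29 gives:
- size 0.098 at 35% and power 0.820 at 55%;
- power 43.1, 64.4, 82.0, 92.9 and 97.9% at true rates of 45, 50, 55, 60 and 65%, matching the table's 43, 64, 82, 93 and 98%.

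That calculation is sound. It concerns RFS and supplies nothing for response. Objectives 1.2.2 and 1.2.4 have no reference rate, target or evaluable number, so there is no comparison to recompute.

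**2. Candidate comparators in the documents.**
- *35% (Section 10.2):* 6-month RFS, primary endpoint.
- *Appendix 4:* 14 rows, with median OS and sometimes PFS in months; no response column.
- *Section 2.4:* says many gliomas responded to PDT, without a rate.
- *Section 2.6.2:* in a 7-patient study of implanted fibers, 2 of 7 were tumor-free beyond 15 months. This is the nearest figure, but it is a long-term tumor-free count after another form of PDT, not a RANO rate, and the plan does not name it as a control.

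**3. Which scan is the baseline.** Section 5.1.2 (pre-treatment evaluation) includes a brain MRI. In Appendix 1 the only brain MRI before Photofrin or illumination falls between Day -30 and Day 0. The next is on Day +2, after both resection and PDT, and Section 5.1.6 gives its purpose as assessing the degree of resection. The pretreatment baseline is therefore most naturally the pre-operative scan.

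**4. Pre-operative baseline.** Partial response needs a fall of more than 50% in measurable enhancing area, held for 4 weeks. Complete response needs all enhancement gone, held for 4 weeks. Resection alone can meet either imaging condition. If the steroid, T2/FLAIR and clinical conditions also hold, surgery is scored as response.

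**5. Post-operative baseline.** Let g be the share of patients with no measurable residual disease on the Day +2 MRI. By the notes in Section 11.3 they can at best be stable, so

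maximum responders = 30 × (1 − g).

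The documents do not give g. For an assumed range:
- g = 30%: 30 × 0.70 = 21
- g = 50%: 30 × 0.50 = 15
- g = 70%: 30 × 0.30 = 9

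The same completely resected patient can thus be a responder under step 4 and at best stable under step 5.

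**6. Precision in the restricted group.** Exact (Clopper-Pearson) 95% intervals, for an assumed observed response rate of 20%:
- 6/30: 7.7 to 38.6%
- 4/20: 5.7 to 43.7%
- 3/15: 4.3 to 48.1%
- 2/10: 2.5 to 55.6%

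These widths suit description, not a claim of superiority over history.

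**The case against.** The strongest defense is that nothing here is promised as a test. Objective 1.2.2 seeks preliminary data, the main task of 1.2.4 is to measure response, and Section 10.4 labels all secondary objectives exploratory. Section 10.4 also never offers Appendix 4 as a response comparator, so the table is not failing at a job it was given. A cited rate could fill the gap. All of this stands, and it limits the weight of the point. It does not supply the missing comparator, and a cited rate alone would not remove the effect of surgery.

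A reader might go further and infer three things that the documents do not support.
- *That fully resected patients cannot have a remission, or that better surgery always lowers the attainable rate.* This holds only with a post-operative baseline and with remission read as RANO CR or PR. On the baseline in Section 11.2 the direction reverses.
- *That the comparison can never be made, or that two of the four secondary objectives are unanswerable.* Resection is limited by neurological safety, so some patients may keep measurable disease and can respond. Response can be measured; only the comparison with history lacks its reference.
- *That a comparison of PFS with Appendix 4 by GBM and AA could take its place.* The rows split by histology give no PFS, and the two talaporfin series that do give PFS are not split by histology.

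**Conclusion.** The point holds in limited form. As written, the plan has no historical rate against which to set remission or response, and it leaves remission undefined. Following Sections 11.2 and 11.3 literally gives a response rate that resection can produce by itself. Moving to the post-operative scan replaces that with a cap equal to the share of patients with measurable residual disease. Neither rate isolates PDT.

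The size depends on that share, which the documents do not give; the 21-to-9-of-30 cap rests on the assumed 30% to 70% and applies only to the post-operative baseline. The absence of a response rate is judged on the text that could be read; the part between Sections 2.6.3 and 2.6.5 was only partly available.

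The affected objectives are exploratory, and the primary endpoint, sample size and test are untouched. The change should be made because it costs little and prevents a misleading claim.

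**What to change.** - In Section 1.2 and the Synopsis, delete the historical comparison of remission from 1.2.2 and the closing historical-control clause from 1.2.4.
- In Section 11.2, name the Day +2 MRI as the baseline for CR and PR. Report them descriptively, only in patients with measurable residual enhancement on that scan, with the denominator stated.
- Leave PFS and OS to objective 1.2.3. In Section 10.4, limit any descriptive reference to Appendix 4 mainly to OS in recurrent disease, and note that the figures come largely from PDT-treated series (12 of the 14 rows are PDT studies).

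**Cost.** Rewording of two objectives and short edits to Sections 10.4 and 11.2. The Day +2 MRI is already required, so no new visits, scans or patients are needed. The claim of a higher remission rate is given up, and the CR/PR denominator falls below 30 if any patient has no measurable residual. Because the Day +2 scan follows illumination, any shrinkage before it is not counted. Other anticancer therapy may start 1 month after PDT (Section 5.2.2), so its start date, already recorded, should be shown beside each response.

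Keeping the comparison instead would require a definition of remission, a named baseline scan and a cited historical response rate from comparably resected patients.
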